7.2.2.2 Assessment of Adverse Events

Investigators will assess the occurrence of AEs and SAEs at all subject evaluation time points during the study. All AEs and SAEs whether volunteered by the subject, discovered by study personnel during questioning, or detected through physical examination, clinically significant laboratory test (ie, requiring change in study drug dose or discontinuation of study drug or any other medical intervention), or other means will be recorded in the subject's medical record and on the AE CRF and, when applicable, on an SAE/Product Complaint form.

Each recorded AE or SAE will be described by its diagnostic term, duration (ie, start and end dates), severity, regulatory seriousness criteria (if applicable), suspected relationship to study drug, and any actions taken.

7.2.2.3 Adverse Events of Special Interest

The following events are adverse events of special interest (AESIs) and must be reported to the sponsor expeditiously (see [Section 7.2.2.7](#) for reporting instructions), irrespective of regulatory seriousness criteria or causality:

- Ventricular arrhythmias (e.g., ventricular extrasystoles, ventricular tachycardia, ventricular arrhythmia, ventricular fibrillation)

7.2.2.4 Second Primary Malignancies

Adverse events (AEs) for malignant tumors reported during a study should generally be assessed as serious AEs (SAEs). If no other seriousness criteria apply, the “Important Medical Event” criterion should be used. In certain situations, however, medical judgment on an individual event basis should be applied to clarify that the malignant tumor event should be assessed and reported as a nonserious AE. For example, if the tumor is included as medical history and progression occurs during the study but the progression does not change treatment and/or prognosis of the malignant tumor, the AE may not fulfill the attributes for being assessed as serious, although reporting of the progression of the malignant tumor as an AE is valid and should occur. Also, some types of malignant tumors, which do not spread remotely after a routine treatment that does not require hospitalization, may be assessed as nonserious; examples in adults include Stage 1 basal cell carcinoma and Stage 1A1 cervical cancer removed via cone biopsy.

The above instruction applies only when the malignant tumor event in question is a new malignant tumor (i.e., it is not the tumor for which entry into the study is a criterion and that is being treated by the IP under study and is not the development of new or progression of existing metastasis to the tumor under study). Malignant tumors that—as part of normal, if rare, progression—undergo transformation (e.g., Richter's transformation of B cell chronic lymphocytic leukemia into diffuse large B cell lymphoma) should not be considered a new malignant tumor.

7.2.2.5 Pregnancy

The investigator should report all pregnancies and pregnancies of the partners of subjects within 24 hours of notification using the Pregnancy Report Form. This form should be faxed or emailed to the AstraZeneca Representative. Any pregnancy-associated SAE must be reported

using the SAE report form, according to the usual timeline and direction for SAE reporting as described below.

Any uncomplicated pregnancy that occurs in a study subject or a partner of a treated subject during this study will be reported for tracking purposes only, if agreed to by the subject or the partner of the subject in this study. All pregnancies and partner pregnancies that are identified during or after this study, wherein the estimated date of conception is determined to have occurred from the time of consent to 2 days after the last dose of acalabrutinib or 90 days after the last dose of ibrutinib (whichever is longer), will be followed to conclusion, and the outcome reported, as long as the subject or partner has consented to participate in follow-up.

Pregnancy itself is not regarded as an AE unless there is suspicion that the investigational product under study may have interfered with the effectiveness of a contraceptive medication. Likewise, elective abortions without complications are not considered AEs. Any SAEs associated with pregnancy (eg, congenital abnormalities/birth defects/spontaneous miscarriage or any other serious events) must additionally be reported as such using the SAE report form.

Subject should be instructed to immediately notify the investigator of any pregnancies. Any female subjects who become pregnant must immediately discontinue study drug. The investigator should counsel the subject, discussing any risks of continuing the pregnancy and any possible effects on the fetus.

Upon completion of the pregnancy, additional information on the mother, pregnancy, and baby will be collected and sent to *the AstraZeneca Representative*.

7.2.2.6 Overdose Instructions

In the event of ingestion of more than the recommended dosage per protocol, additional clinical monitoring is recommended by the sponsor. For any subject experiencing an acalabrutinib or ibrutinib overdose (ingestion of more than the recommended dosage), observation for any symptomatic side effects should be instituted, and vital signs, biochemical and hematologic parameters should be followed closely (consistent with the protocol or more frequently, as needed). Appropriate supportive management to mitigate adverse effects should be initiated. If the overdose ingestion of acalabrutinib or ibrutinib is recent and substantial, and if there are no medical contraindications, use of gastric lavage or induction of emesis may be considered.

The medical monitor must be contacted if a study drug overdose occurs.

7.2.2.7 Expedited Reporting Requirements for Serious Adverse Events/Adverse Events of Special Interest

All SAEs/AES/s must be reported within 24 hours of discovery. All initial SAE/AES/s reports and follow-up information will be reported using the protocol-specific electronic data capture system. If electronic SAE/AES/s reporting is not available, paper SAE/AES/s report forms must be sent to the AstraZeneca Representative, or designee. The AstraZeneca Representative may request follow-up and other additional information from the investigator (eg, hospital admission/discharge notes and laboratory results).

Whenever possible, SAEs/AES/s should be reported by diagnosis term not as a constellation of symptoms. All deaths should be reported with the primary cause of death as the AE term, as death is typically the outcome of the event, not the event itself. The primary cause of death on the autopsy report should be the term reported. Autopsy and postmortem reports must be forwarded to the AstraZeneca Representative, or designee, as outlined above.

If study drug is discontinued because of an SAE/AES/s, this information must be included in the SAE/AES/s report.

An SAE/AES/s may qualify for mandatory expedited reporting to regulatory authorities if the SAE/AES/s is attributable to the study drug and is not listed in the current Investigator Brochure (ie, an unexpected event). In this case, Acerta Pharma will forward a formal notification describing the suspected unexpected serious adverse reaction (SUSAR) to all investigators. Each investigator must then notify his or her IRB/IEC of the SUSAR.

7.2.2.8 Other Safety Issues Requiring Expedited Reporting

For studies being conducted in Europe, expedited reporting is required for safety issues that might materially alter the current benefit-risk assessment of an investigational medicinal product or that would be sufficient to consider changes in the investigational medicinal products administration or in the overall conduct of the trial. For a detailed description of safety issues that may qualify for expedited reporting please refer to the European Commission guidance titled, "Detailed guidance on the collection, verification and presentation of adverse reaction reports arising from clinical trials on medicinal products for human use – April 2006" available at http://ec.europa.eu/health/files/eudralex/vol-10/21_susar_rev2_2006_04_11_en.pdf.

7.2.2.9 Hy's Law

Cases where a subject shows elevations in liver biochemistry may require further evaluation, and occurrences of AST or ALT $\geq 3 \times \text{ULN}$ together with total bilirubin $\geq 2 \times \text{ULN}$ may need to be reported as SAEs. Refer to [Appendix J](#) for further instruction on cases of increases in liver biochemistry and evaluation of Hy's law.

7.2.3 Reporting of Serious Adverse Events by Sponsor

Regulatory Authorities, IRBs/IECs, and Investigators will be notified of SAEs in accordance with applicable requirements (eg, GCP, ICH guidelines, national regulations, and local requirements). For the purpose of this protocol, Acerta Pharma considers acalabrutinib and ibrutinib as investigational agents and will follow applicable guidelines for reporting SAEs for both drugs.

8 WITHDRAWAL OF SUBJECT FROM TREATMENT OR ASSESSMENT

8.1 WITHDRAWAL OF SUBJECTS FROM STUDY TREATMENT

Subjects may be withdrawn from study treatment for the following reasons:

- Any subject who has objective evidence of disease progression while receiving protocol-required study drug should be withdrawn from the study treatment. If there is uncertainty regarding whether there is disease progression, the subject may continue study treatment and remain under close observation (eg, evaluated at 2- to 4-week intervals) pending IRC confirmation of disease progression. In particular, transient worsening of disease during temporary interruption of study therapy (eg, for drug-related toxicity, surgery, or intercurrent illness) may not indicate disease progression. In such circumstances, and if medically appropriate, subjects may resume therapy and relevant clinical, laboratory, and/or radiologic assessments should be done to document whether tumor control can be maintained or whether actual disease progression has occurred.
- Toxicity as defined in dose discontinuation sections of the protocol
- Withdrawal from treatment by subject including withdrawal of informed consent
- Drug hold > 28 days
- Second primary malignancy necessitating systemic treatment
- Pregnancy in a subject
- Investigator decision
- Requires prohibited treatment
- Study terminated by sponsor

8.2 REASONS FOR STUDY EXIT

Reasons for study exit include:

- Subject's withdrawal of consent from study
- Decision by sponsor to terminate the study
- Subject lost to follow-up
- Death

In case a subject is lost to follow-up, every reasonable effort must be made by the study site personnel to contact the subject and determine the reason for discontinuation. The measures taken to follow up must be documented.

When a subject withdraws before completing the study, the reason for withdrawal *and scope of withdrawal (e.g., complete or only from treatment and/or protocol assessments)* must be documented in the CRF and in the source documents. Subjects who withdraw consent should still be encouraged to complete the safety follow-up assessments before withdrawing consent, but these assessments cannot be mandated once consent is withdrawn. *In cases of partial withdrawal of consent, subjects should be encouraged to allow future contact for survival follow-up.*

Subjects who are withdrawn or removed from study treatment will not be replaced.

9 STATISTICAL METHODS

9.1 GENERAL CONSIDERATIONS

The statistical and analytical plans presented below summarize the more complete plans to be detailed in the statistical analysis plan (SAP). A change to the data analysis methods described in the protocol will require a protocol amendment only if it alters a principal feature of the protocol. The SAP will be finalized before database lock. Any changes to the methods described in the final SAP will be described and justified in the clinical study report.

Independent Review Committee

The IRC will be chaired by a physician with expertise in CLL and will conduct response evaluations in accordance with the IRC charter.

Data Monitoring Committee

A DMC, chaired by a physician with expertise in CLL, will monitor the safety of the subjects in this study. An early safety analysis will be performed after approximately 50 subjects have been treated for approximately 8 weeks. This analysis will focus on deaths, treatment discontinuations, SAEs, and Grade 3/4 AEs as well as special events of interest. The Medical

Monitor will review, in a blinded fashion, this information on an ongoing basis until this early safety analysis is conducted. Detailed information on the role of the DMC and frequency of meetings, which occur at least every 6 months, will be provided in the DMC charter separate from this protocol.

9.2 RANDOMIZATION

This study will use an IWRS for randomization. Subjects will be randomized in a 1:1 ratio to receive either acalabrutinib or ibrutinib with the following stratification factors:

- Presence of 17p del
- ECOG performance status (ECOG = 2 versus ECOG \leq 1)
- Number of prior therapies (1-3 versus \geq 4)

The treatment assignment for any individual study subject will not be known to study and site personnel or the subject before subject randomization into the study.

9.3 DETERMINATION OF SAMPLE SIZE

A recently completed trial that studied PFS in CLL (Byrd 2014) showed that ibrutinib (the reference/comparator drug in Protocol ACE-CL-006) was superior to ofatumumab, a drug approved for the treatment of CLL in patients with previously treated CLL. Superiority in that study was shown in the overall study population (HR=0.21) as well as in patients with 17p del (HR=0.25) or 11q del (HR=0.14).

Protocol ACE-CL-006 is designed to have 80% power to show that the upper bound of a 2-sided 95% CI for PFS is < 1.429 (the NI bound).

With randomization in a 1:1 ratio, the trial will require approximately 250 events if acalabrutinib and ibrutinib are truly equally effective. Assuming an enrollment period of about [CCI] and a follow-up period of approximately [CCI] after the last subject enters the study, the estimated sample size is 500 subjects (250 per arm).

9.4 ANALYSIS POPULATIONS

Intent-to-Treat (ITT) Population

The ITT population will be defined as all subjects randomized.

All efficacy analysis will be performed in the ITT population and will be analyzed as randomized. In addition, the ITT population will be used to summarize demographics, and baseline and disease characteristics.

Safety Population

The safety population includes all subjects who received at least one dose of study drug. The safety population will be the analysis population for the safety analyses. Subjects will be analyzed as treated.

CCI [REDACTED]

CCI [REDACTED]

CCI [REDACTED]

CCI [REDACTED]

9.5 HANDLING OF MISSING VALUES/CENSORING/DISCONTINUATIONS

Missing or partial start and end dates for AEs and concomitant medications will be imputed according to prespecified, conservative imputation rules. The SAP will describe the details for handling missing data.

9.6 EFFICACY ANALYSES

9.6.1 Primary Endpoint and Methods

The primary efficacy endpoint is PFS, which is defined as the time from the date of randomization until disease progression (assessed by the IRC per IWCLL 2008 criteria) or death from any cause, whichever occurs first. The primary analysis is event-based and will be conducted after enrollment is completed and approximately 250 IRC-assessed events have occurred.

The primary analysis for this study will be conducted to assess whether acalabrutinib is non-inferior to ibrutinib with respect to PFS based on comparison of the upper bound of the 95% CI of HR to the prespecified NI margin of 1.429. The two-sided 95% CI for the HR of acalabrutinib versus ibrutinib will be estimated using a stratified Cox proportional hazard model.

Additional sensitivity and subgroup analyses may be conducted and will be described in SAP.

9.6.2 Secondary Endpoints and Methods

If acalabrutinib is shown non-inferior to ibrutinib, the secondary endpoints will be tested in manner that maintains the Type I error rate at $\leq 5\%$. The SAP will describe the methodology to be used for multiplicity adjustment.

Grade ≥ 3 Infections, Richter’s Transformation, and Atrial Fibrillation

The incidences of treatment-emergent Grade ≥ 3 infections, Richter’s transformation, and atrial fibrillation will be summarized and compared between the 2 treatment arms using 2-sided Cochran-Mantel-Haenszel tests adjusted for the randomization strata.

Richter’s transformation will be assessed by central pathology. Incidence of Grade ≥ 3 infections and atrial fibrillation will be collected as described for all AEs ([Section 7.2.2](#)).

Overall Survival

Differences between the treatment arms in OS will be assessed using Kaplan-Meier methods and a stratified log-rank test. Medians, ranges, hazard ratios and corresponding 95% CIs will be presented. The OS HR and its 95% CI will be presented using a stratified Cox regression model.

9.6.3 Exploratory Endpoints

CCI [Redacted]

[Redacted]

CCI [Redacted]

[Redacted]

Other Exploratory Endpoints

CCI [Redacted]

CCI

9.7 SAFETY ANALYSES

Safety data will be summarized for the safety population. The baseline value for safety analysis is defined as the value collected at the time closest to and before the start of study drug administration.

Adverse Events

AEs will be graded by the investigator according to the National Cancer Institute (NCI) CTCAE v4.03 or higher for non-hematologic AEs. Hematologic toxicity will be assessed by the grading scale for hematologic toxicity in CLL studies in the IWCLL 2008 guidelines. Each AE verbatim term will be coded to a system organ class and a preferred term using the Medical Dictionary for Regulatory Activities (MedDRA).

Treatment-emergent Adverse Events

All TEAEs will be summarized by treatment arm as treated. In addition, AE incidence rates will also be summarized by severity and relationship to study drug.

Grade 3 or Grade 4 TEAEs; TEAEs leading to permanent study drug treatment discontinuation; TEAEs leading to dose reduction; serious TEAEs; TEAEs of special interest and TEAEs resulting in death will be summarized by treatment arm as treated.

Clinical Laboratory Tests

Data Summary Methods:

For gradable parameters, a summary of worst post baseline toxicity grade will be provided in the treatment-emergent period and worst toxicity grade (any grade and Grade 3/4). The difference between groups in percentages will be displayed.

Liver function abnormality by Hy's law and frequencies of abnormal treatment emergent uric acid will be summarized.

Analysis of Lymphocytosis:

For all subjects with baseline and any post-baseline ALC measurements, ALC at peak summary will be provided by treatment arm. *Median percentage change in ALC from baseline with its 95% CI will also be displayed graphically over time.*

CCI [Redacted]
[Redacted]
[Redacted] CCI [Redacted]
[Redacted]

CCI [Redacted]
[Redacted]
[Redacted]
[Redacted]
[Redacted]
[Redacted]
[Redacted]

CCI [Redacted]
[Redacted]
[Redacted]
[Redacted]
[Redacted]

ECOG Performance Status

ECOG performance status will be collected as scheduled in [Appendix A](#). ECOG performance status grade ranges from 0 to 5. Descriptive statistics will be provided for each visit over time.

Vital Signs and Weight

Body temperature, heart rate (beats/min), systolic blood pressure (mmHg), diastolic blood pressure (mmHg), respiratory rate (breaths/min), and weight will be collected as scheduled in [Appendix A](#). For each parameter, descriptive statistics will be provided over time.

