- An aggregate analysis of specific events that can be anticipated to occur in the study population independent of drug exposure. Such events include known consequences of the underlying disease or condition under investigation (eg, symptoms or disease progression), or events unlikely to be related to the underlying disease or condition under investigation, but commonly occur in the study population independent of drug therapy (eg, cardiovascular events in an elderly population). An aggregate analysis (across studies) will identify those events that occur more frequently in the drug treatment group than in a concurrent or historical control group.

This definition of “suspected adverse reaction” and the application of the “reasonable possibility” causality standard is considered to be consistent with the concepts and discussion about causality in the ICH E2A guidance ([FDA Guidance for Industry 1995](#)).

Severity

Definitions found in the Common Terminology Criteria for Adverse Events (CTCAE) version 4.03 or higher will be used for grading the severity (intensity) of nonhematologic AEs. The CTCAE v4.03 displays Grades 1 through 5 with unique clinical descriptions of severity for each referenced AE. Should a subject experience any AE not listed in the CTCAE v4.03 or higher, the following grading system should be used to assess severity:

- Grade 1 (Mild AE) – experiences which are usually transient, requiring no special treatment, and not interfering with the subject’s daily activities
- Grade 2 (Moderate AE) – experiences which introduce some level of inconvenience or concern to the subject, and which may interfere with daily activities, but are usually ameliorated by simple therapeutic measures
- Grade 3 (Severe AE) – experiences which are unacceptable or intolerable, significantly interrupt the subject’s usual daily activity, and require systemic drug therapy or other treatment
- Grade 4 (Life-threatening or disabling AE) – experiences which cause the subject to be in imminent danger of death
- Grade 5 (Death related to AE) – experiences which result in subject death

The grading scale for hematologic toxicity in subjects with CLL is provided in Appendix E.

Causality

The causality of AEs to the study drug will be assessed by means of the question: ‘Is there a reasonable possibility that the event may have been caused by the study drug?’ per FDA guidance on safety reporting requirements ([FDA Guidance 2012](#)).

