### **8.1.1 Treatment Emergent Adverse Events**

TEAE is defined as an adverse event reported during the treatment emergent period (defined in Section 4.1.6). Any ongoing event that worsens in severity after the first dose date of study drug is also defined as a TEAE. Incomplete onset dates will be imputed as detailed in Section 4.2, for the purpose of determining whether AEs are treatment emergent.

TEAEs will be tabulated in summary tables by treatment arm. For each treatment arm, frequency and percentage of adverse events within each system organ class and preferred term will be presented. The denominator for the adverse event incidence will be based on the number of safety population subjects in that treatment arm, unless otherwise specified. Adverse event incidence rates will also be summarized by severity and relationship to study drug based on the investigator’s judgment.

Subjects with multiple occurrences of events for a given preferred term, system organ class, or overall will be counted only once at the maximum severity and strongest relationship to study drug, respectively, for each preferred term and system organ class.

In addition, Grade 3 or Grade 4 TEAEs, TEAEs that led to permanent study drug discontinuation, TEAEs that led to dose reduction, TEAEs that led to dose interruption, serious TEAEs, and TEAEs that resulted in death will be summarized by treatment arm as treated.

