### **8.1.4 Subgroup Analyses for Adverse Events**

Subgroup analyses will be performed for TEAEs using the same subgroups used for the primary endpoint subgroup analyses (listed in Section 7.1.4) to investigate benefit:risk for acalabrutinib versus ibrutinib.

For each of the TEAE types listed below, the risk difference (Arm A – Arm B) and its corresponding 95% CI for each subgroup will be calculated based on normal approximation (with use of Wilson's score) and displayed graphically in a forest plot. Additional subgroups may be considered as appropriate.

- Grade  $\geq 3$  TEAEs
- TEAEs leading to dose interruption
- TEAEs leading to discontinuation of treatment

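### The by-arm severe-TEAE summary stops at Grade 4, so fatal events can drop out of it, while the SAP's own subgroup plot and infection endpoint use Grade ≥3

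*Protocol*

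**What the plan says.** Protocol 9.7 plans by-arm summaries of "Grade 3 or Grade 4 TEAEs; TEAEs leading to permanent study drug treatment discontinuation", followed by other categories that end with "TEAEs of special interest and TEAEs resulting in death will be summarized by treatment arm as treated". SAP 8.1.1 repeats the grade limit: "In addition, Grade 3 or Grade 4 TEAEs, TEAEs that led to permanent study drug discontinuation". It too keeps a separate fatal category: "TEAEs that resulted in death will be summarized by treatment arm as treated".

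Earlier in SAP 8.1.1 there is a counting rule: "Subjects with multiple occurrences of events for a given preferred term, system organ class, or overall will be counted only once at the maximum severity". A matching rule applies to relationship to study drug.

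Protocol 7.2.1 describes CTCAE v4.03 as running from Grade 1 to Grade 5. Its fallback scale for events that CTCAE does not list ends with "Grade 5 (Death related to AE) – experiences which result in subject death". A fatal event therefore has its own grade above Grade 4.

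Elsewhere the SAP uses a different cut-off. Section 8.1.4 begins "For each of the TEAE types listed below, the risk difference" and puts Grade ≥3 TEAEs first in its list. The infection endpoint in SAP 2.6 and 7.2.1 is also Grade ≥3. Both include fatal events.

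**The concern.** A summary of severe toxicity should not look better because an event became fatal. If the maximum-severity rule is applied to a table limited to Grades 3 and 4, a subject with a Grade 3 pneumonia and a later fatal pneumonia is classed at Grade 5 and appears in neither counted grade. In the overall row the same happens to every subject with a fatal TEAE, whatever other severe events that subject had. The loss is greater in the arm with more fatal TEAEs, so the distortion has a direction.

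There is also an internal mismatch. The subgroup plots in SAP 8.1.4 would show Grade ≥3 risk differences, but no whole-population Grade ≥3 TEAE summary is named for comparison. SAP Appendix 1 defines infections by the infections system organ class. If the Grade 3 or 4 table is laid out by system organ class, as SAP 8.1.1 describes for its TEAE tables, one report would carry two different severe-infection counts for the same class, population and period.

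Fatal cases are foreseeable. The protocol reports fatal infections with both drugs (6.2.5.3, 6.2.10.2) and fatal haemorrhage with acalabrutinib (6.2.5.2). The secondary objectives in Protocol 3.2.1 are framed as benefit:risk in an open-label trial, so by-arm severity tables will be read closely.

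**Working it through.** The documents give no expected rate of Grade ≥3, Grade 3 or 4, or fatal TEAEs, so there is no plan figure to reproduce. The check is counting arithmetic. All rates below are assumptions. The 250 per arm is the planned size, used as an approximation to the safety population.

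**Notation.** G is the proportion of an arm with any Grade ≥3 TEAE. F is the proportion with a fatal (Grade 5) TEAE. q is the share of fatal cases that have no Grade 3 or 4 TEAE.

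**Reading A: the maximum-severity rule governs the table.** Overall Grade 3 or 4 row = G − F. The difference between arms (second minus first) is (G2 − G1) − (F2 − F1).

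Equal Grade ≥3 incidence, G = 65% in both arms, F = 5% and 10%:
- First arm: 65 − 5 = 60%.
- Second arm: 65 − 10 = 55%.
- The true Grade ≥3 difference is 0. The table shows 5 points in favour of the arm with more fatal TEAEs, or 0.05 × 250 = 12.5 subjects.

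With equal G, the false difference is F2 − F1 and does not depend on G. For fatal rates of 3% and 6% it is 3 points; for 6% and 12% it is 6 points.

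Unequal Grade ≥3 incidence, first arm fixed at G = 65% and F = 5% (row 60%), second arm F = 10%:

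| G, second arm | True Grade ≥3 excess | Row, second arm | Table shows |
|---|---|---|---|
| 65% | 0 | 55% | false 5-point deficit |
| 68% | 3 points | 58% | reversed, 2-point deficit |
| 70% | 5 points | 60% | excess masked |
| 72% | 7 points | 62% | excess shrunk to 2 points |

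Reversal occurs only when F2 − F1 exceeds G2 − G1.

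**Reading B: the table counts any subject with at least one Grade 3 or 4 TEAE.** Row = G − qF. With equal G, the false difference is q × (F2 − F1). For F = 5% and 10%:
- q = 20%: 0.20 × 5 = 1.0 point.
- q = 50%: 0.50 × 5 = 2.5 points.

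The direction is the same and the size is smaller.

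**Can the total be recovered?** Under Reading A the overall categories are exclusive, so adding the fatal-TEAE percentage restores G exactly: 60 + 5 = 65% and 55 + 10 = 65%. Under Reading B the same addition counts twice those subjects who had both a Grade 3 or 4 and a fatal TEAE. The plan does not say which reading applies, so a reader of these two tables alone cannot tell whether adding is valid. SAP 8.1.1 and Protocol 9.7 also plan a summary by severity that is not limited to Grades 3 and 4. With each subject counted once overall at maximum severity, the sum of Grades 3, 4 and 5 in that summary gives the Grade ≥3 incidence.

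**The case against.** The best defence is that the maximum-severity rule was not written for this table. In SAP 8.1.1 it follows the sentence on summaries by severity and relationship, and mirrors it. The Grade 3 or 4 item comes in a new paragraph whose other items are event filters: serious, led to discontinuation, led to dose reduction. Reading it as any Grade 3 or 4 event is at least as natural. Protocol 9.7 contains no maximum-severity rule. This stands: the 5-point figure belongs to one of two readings, and the other gives 1 to 2.5 points.

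A second defence is that nothing is lost from the report. Fatal TEAEs, serious TEAEs, TEAEs by severity and all deaths by cause (SAP 8.2) are tabulated by arm. This also stands. A reader might infer that the Grade ≥3 total cannot be rebuilt, but the documents do not support that: under Reading A simple addition works, and under either reading the by-severity summary largely supplies it.

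A reader might also infer that the arm with more deaths must show fewer severe AEs. That does not follow. Reversal depends on the condition shown above, and only TEAEs with a fatal outcome matter. Deaths outside the treatment-emergent period (SAP 4.1.6) leave the table unchanged.

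Nor do the documents rank this table above the other safety outputs. It is descriptive. The gate-kept tests include Grade ≥3 infections and OS, and neither excludes fatal events.

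These points limit the consequence. They do not remove the mismatch with SAP 8.1.4, or the silence on how a subject with both a Grade 3 or 4 and a Grade 5 event is counted.

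**Conclusion.** The point holds as a low-weight reporting improvement. Both documents limit the by-arm severe-TEAE summary to Grades 3 and 4, while the SAP uses Grade ≥3 for its subgroup plots and infection endpoint. Leaving out Grade 5 lowers the row more in the arm with more fatal TEAEs. That arm's excess can be understated, or reversed if its fatal excess is larger than its Grade ≥3 excess.

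With equal Grade ≥3 incidence and fatal rates of 5% and 10%, the false difference is 5 points under maximum-severity counting. It is about 1 to 2.5 points under any-event counting if 20% to 50% of fatal cases have no Grade 3 or 4 event. These rates are assumed, and the choice between the two readings is open in the text. No test in the hierarchy changes.

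**What to change.** In SAP 8.1.1, replace the Grade 3 or 4 category with *Grade ≥3 TEAEs (including Grade 5)*, reported by system organ class, preferred term and overall. The overall row then matches the definition behind the SAP 8.1.4 plots. Keep the separate table of fatal TEAEs. If a Grade 3 or 4 table is also retained, state that a subject with at least one Grade 3 or 4 TEAE is counted regardless of any Grade 5 event.

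Protocol 9.7 can be aligned at the next amendment. Protocol 9.1 requires an amendment only when a principal feature changes, and this is not one.

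The cost is one phrase and no new data. The reported percentage in each arm rises by the fatal cases now included.
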